Enrolled patients and their families will be randomized 1:1 after discharge to the intervention group or standard-of-care using a permuted block randomization stratified by acute versus chronic underlying illness and hospitalist service general vs. surgical service to ensure equal allocation of the intervention within each stratification block. Random permutations within each block within each stratum will be generated using a random number generator available in SAS Proc Plan. The use of randomization in the study design is crucial for avoiding bias in the evaluation of the effectiveness of the nurse home visit intervention. Patients and families cannot be blinded given that the nature of the intervention is a nurse home visit. However, we will attempt to mitigate the potential bias in the following manner: 1) Families will be asked to refrain from disclosing intervention status to the interviewer at the follow-up phone call; and 2) Study staff will be blinded to treatment assignment when making the follow-up phone call. Study staff will use a written script to administer the survey. At the start of the call, families will be reminded to refrain from disclosing their intervention status.

Heterogeneity of Treatment Effects:

We have multiple planned analyses to examine potential heterogeneity of treatment effect of the nurse visit. Factors included in the HET analysis are insurance, primary care access, financial strain, caregiver education, hospital service, and medical complexity. Medical complexity will be determined by the pediatric medical complexity algorithm (PMCA). The PMCA is a publicly available algorithm that identifies children with complex chronic disease (who have accessed tertiary hospital care). The algorithm includes three levels of medical complexity: children with complex chronic disease (C-CD), children with non-complex chronic disease (NC-CD), and children without chronic disease (CD). In order to calculate the PMCA we will collect additional administrative data for all patients enrolled in Aims 3 and 4. This data will include: ICD9 Codes/ICD10 codes, procedure codes, admission date, discharge dates, admitting and discharge departments. We will capture all outpatient, urgent care, ED, and hospital events within the specified time window (February 1, 2012 to April 30, 2016). The PMCA will be calculated based on a 3-year window before the index hospitalization.

Aim 4

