In all cases, secondary analyses will be performed including potential covariates, which may affect the impact of the intervention. We will look at the association between both the dependent variable of interest and the potential covariate/confounder and between the intervention and the potential covariate or confounder. Those associated with either the dependent variable or the intervention at p<0.15 will be entered into the initial model. Backward elimination will be used, variables significant at p<0.05 and those involved in confounding (i.e., if elimination from the model changes the beta coefficient for the intervention by more than 10%) will be retained in the model. Variables considered as potential covariates are patient age, parent or caregiver age, education, marital status, household income, employment status, and access to primary care.

Additional secondary analyses of the reutilization rate will exclude unforeseen readmissions for newly developed conditions not related to known diseases during the index hospitalization. In addition to the intent to treat analysis, a per-protocol analysis will also be employed. Analysis of secondary outcomes identified through Aim 1 will be tailored to the outcome measure. For example, if parents or caregivers identify days of work missed as an important outcome, our analysis of days of work missed will be restricted to only those parents/caregivers reporting work outside the home. We will take a two-part approach to analysis. First, we will treat it as a binary outcome, comparing the percentage of caregivers that missed at least one day of work during the 30-day follow-up period between the two study arms using logistic regression. Second, we will treat the number of days of work missed as a count outcome and use poisson regression to compare the two study arms. No interim analysis is planned.

Heterogeneity of Treatment Effects:

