Official Title: Supplement to Hospital to Home Outcomes (H2O): A Study to Improve the Fluidity of Transitions Between Hospital and Home

NCT: 03224130

Date: 20 September 2018

H2O Statistical Analysis Plan for Supplement (AIM 4)

Prepared by:

[name]

[name]

Date:

11/3/2016

Analysis plan approved by:

[name], MSCE

Professor, Division Director

Division of Hospital Medicine

PI H2O

The results of H2O Supplement (Aim 4) will be assessed as described in this document. This statistical analysis plan begins with an overview of the key components of the study including its design, objectives, and outcome measures. This is followed by a detailed description of the statistical analyses that will be utilized to address H2O Supplement Grant Aim 2 study hypotheses.

- 1. Overview of study: This study is single center, parallel, randomized trial to evaluate the effectiveness of a nurse phone call. Patients that meet eligibility criteria will be randomized 1:1 to receive either the intervention group (a nurse phone call within 96 hours of discharge) or the control group (standard-of-care). The randomization scheme utilized permuted block with two stratification factors, SES and state, to ensure equal allocation of the intervention within each stratification block. Random permutations within each block within each stratum were generated using a random number generator available in SAS Proc Plan. The planned enrollment is a total of 900 patients with enrollment ending October 31, 2016.
- **1.1 Study Objective**: To evaluate the effectiveness of a nurse-led telephone intervention for families following their child's hospitalization for acute illness.

Working hypothesis 1: Patients who receive the nurse phone call will have a significantly lower occurrence of any unplanned re-hospitalization and/or any emergency/urgent care visits within 30 days of hospital discharge compared to the patients enrolled in the standard-of-care group.

Working hypothesis 2: Patients who receive the nurse phone call will have significantly better post discharge coping difficulty scores and faster return to normalcy compared to patients in the standard-of-care group.

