2.3.2 Primary outcome analysis

Primary outcome: unplanned re-hospitalization and/or any emergency/urgent care visits within 30 days of hospital discharge

For the primary outcome, the dependent variable will be a dichotomized indicator of any occurrence of unplanned re-hospitalization and/or any emergency/urgent care visits within 30 days of hospital discharge recorded in CCHMC Epic or Healthbridge for non-CCHMC events. Differences between intervention and control groups on this outcome will be evaluated using logistic regression with the stratification variables (census tract poverty and state of residence). Other potential covariates (e.g. baseline characteristics of age, first hospitalization, only child, caregiver education, with large differences between groups) will be included in a secondary analysis model evaluating the effectiveness of the intervention.

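### Prior ED, urgent care and hospital use is collected only to derive the medical complexity class; one prespecified prior-use covariate in the Aim 4 primary model would add a little power, provided the extract is extended

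*Protocol*

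**What the plan says.** **Collection.** The heterogeneity paragraph appears under Study Design, Aim 3 and again under Data Analysis/Methods. It says: "In order to calculate the PMCA we will collect additional administrative data for all patients enrolled in Aims 3 and 4". It then says "We will capture all outpatient, urgent care, ED, and hospital events within the specified time window", the window being "February 1, 2012 to April 30, 2016". The look-back is stated as "The PMCA will be calculated based on a 3-year window before the index hospitalization". No other use of these events is given.

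**Aim 4 models.** SAP 2.3.2 specifies "logistic regression with the stratification variables (census tract poverty and state of residence" for the primary outcome. The protocol's Aim 4 analysis section has poverty and discharge service unit instead. Age, first hospitalization, only-child status and caregiver education are examples of covariates for a secondary model, to be used where the arms differ greatly. SAP 2.3.1 has the same imbalance rule, and neither section defines a large difference. The SAP subgroups (1.3 and 2.3.4) do not include medical complexity, so the Aim 4 SAP uses neither the event history nor the class derived from it.

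**Aim 3 models.** The primary model adjusts for chronic condition and service. For secondary models the protocol says: "Variables considered as potential covariates are patient age, parent or caregiver age, education, marital status, household income, employment status, and access to primary care". No prior-use variable is on that list.

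**Timing.** SAP section 1: "The planned enrollment is a total of 900 patients with enrollment ending October 31, 2016". The SAP is dated 3 November 2016. SAP 2.4 says the supplement did not enroll in winter, and for that reason excludes November to April discharges from the four-arm comparison.

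**The concern.** ED, urgent care and hospital events before the index stay are the same broad kinds of event that the primary outcome counts afterwards. The protocol's own background gives reason to expect use to cluster within children: 2.9% of patients had four or more readmissions and accounted for 18.8% of admissions over a year. A variable fixed before randomisation that predicts the outcome can raise the power of the treatment test and correct for chance imbalance between the arms. Here such a variable could be built largely from data the study already plans to collect, yet no model names it.

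The SAP's substitute is weaker. A yes/no indicator that enters only when the arms look different, by an undefined standard, lets observed imbalance choose the covariate. Naming one covariate in advance avoids that choice.

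**Working it through.** **1. The plan's own figure.** Inputs from the protocol's Aim 4 sample size paragraph: 750 control, 450 phone call, 20% versus 12.9%, alpha 0.05, 11% noncompliance. A two-sided test is assumed, since it is stated only for the secondary outcomes. Noncompliance dilutes the difference to 0.071 × 0.89 = 0.0632, so the treated rate is 0.1368.

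Power = Φ[(d − 1.96·SE0)/SE1], with SE0 from the pooled rate and SE1 from the separate rates:
- Pooled rate = (750 × 0.20 + 450 × 0.1368)/1200 = 0.1763
- SE0 = √[0.1763 × 0.8237 × (1/750 + 1/450)] = 0.0227
- SE1 = √[0.16/750 + 0.1368 × 0.8632/450] = 0.0218
- Power = 80.4%, against 80% stated. The figure reproduces.

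The SAP's 900 patients at 1:1, taken as 450 per arm, give 71.7% with the same dilution, or 82.0% without it.

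**2. Assumed gradients.** The documents give none. Three prior-use groups are assumed, with an overall control risk of about 20%. Share of outcome variance explained: R² = Σ share × (risk − 0.199)² / (0.2 × 0.8), where 0.199 is the mean of the rounded risks.

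| Gradient | Shares (%) | Risks (%) | R² |
|---|---|---|---|
| Weak | 60/30/10 | 17/22/31 | 0.0019/0.16 = 0.012 |
| Moderate | 50/35/15 | 13/22/38 | 0.0074/0.16 = 0.047 |
| Strong | 50/35/15 | 10/22/48 | 0.0169/0.16 = 0.106 |

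The strong case is extreme: its top-to-bottom odds ratio is (0.48/0.52)/(0.10/0.90) = 8.3. For comparison, a yes/no covariate with prevalence 10–50% and odds ratio 1.5–3 gives R² of only 0.003 to 0.048.

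**3. Power by simulation.** 450 per arm, 20% versus 12.9%, logistic Wald test with and without the prior-use factor. Baseline power is about 82%. Across repeated runs of at least 4,000 trials, the gain was about 0–0.5 points (weak), 1–2 (moderate) and 3–5 (strong). With dilution, one set of runs gave 71.1% to 71.3%, 72.0% to 73.7% and 73.4% to 77.0%.

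**4. Power by formula.** Treating adjustment as an effective sample of N/(1 − R²), with dilution:

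| R² | 750/450 | 450/450 |
|---|---|---|
| 0 | 80.4% | 71.7% |
| 0.01 | 80.8% | 72.2% |
| 0.05 | 82.4% | 73.9% |
| 0.10 | 84.4% | 76.2% |

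**5. Interval width.** In the simulations the standard error of the treatment log odds ratio rose with adjustment, from 0.184 to 0.186, 0.189 and 0.195. Power improves because the conditional odds ratio moves further from 1 by more than its standard error grows. For a standardised risk difference the width changes by 1 − √(1 − R²): 0.25% narrower at R² = 0.005, 2.5% at 0.05 and 5.1% at 0.10.

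**6. Chance imbalance.** With 450 per arm, a two-SD imbalance in the share of top-group children is 2√(0.10 × 0.90 × 2/450) = 0.040 (weak) or 2√(0.15 × 0.85 × 2/450) = 0.048 (moderate, strong). Multiplied by the risk gap between the top group and the rest (0.12, 0.21, 0.33), this shifts the crude risk difference by about 0.5, 1.0 or 1.6 points, against the 7.1-point target.

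**7. Does the extract cover the look-back?** It closes on 30 April 2016 and Aim 4 enrolled to 31 October 2016. A child admitted at the end would lack 184 days, about half of a 12-month look-back. The Aim 4 start date is not given, so the share of children affected is unknown.

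**The case against.** The strongest reply is that nothing here is an error. Adjusting for the stratification factors is valid under randomisation, no error rate is affected, and the gain is small. That stands. A reader might infer that the primary comparison is biased or invalid without the covariate; the documents do not support that.

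A reader might also infer that the study already holds, for every child and at no cost, the baseline value of its own outcome. That goes too far, for three reasons:
- The window ends before Aim 4 enrollment does.
- SAP 1.2 defines unplanned CCHMC admissions by the gap between scheduling and admission. The protocol's list of extracted fields has no scheduling time, so that rule cannot be applied to the history as described. Aim 3 also counts unscheduled follow-up.
- The outcome draws on HealthBridge for events outside CCHMC, and no such capture is described for the history. The SAP's data management appendix lists Epic readmission and revisit data within 30 days of discharge, and no pre-index events.

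A third tempting reading is that the planned odds ratio would become more precise. Step 5 shows the opposite for its standard error.

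Imbalance is not wholly unaddressed. The SAP can bring in first hospitalization, the protocol plans a covariate for Health Network services, and Aim 3 adjusts for chronic condition, which may absorb part of any prior-use signal. Aim 4 also excludes children eligible for traditional home care, which may thin out heavy users.

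Timing limits the fix too. The SAP is dated after enrollment closed, and the protocol already reports Aim 3 results.

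**Conclusion.** The point holds as a modest, low-cost improvement to the analysis. The history is collected with one stated use, and no effectiveness model includes a prior-use count. The gain is about 0 to 5 points of power at 450 per arm, and likely 2 or fewer, because the larger figures need a gradient that nothing in the documents supports. Precision improves only for a standardised risk difference, by about 0.3–2.5% for R² of 0.005 to 0.05. All of this rests on assumed gradients, on 450 per arm, and on CCHMC events standing in for all prior use.

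The larger power question is separate. The protocol's sample size paragraph has 750 and 450, its Aim 4 design section has 1:1, and the SAP has 1:1 with 900 patients. With dilution that is 80.4% against 71.7%, a bigger gap than this covariate could close. Those passages need to be reconciled.

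**What to change.** 1. In SAP 2.3.2, before outcomes are examined by arm, add to the primary Aim 4 logistic model one prespecified count of CCHMC ED, urgent care and hospital events in the 12 months before the index admission (0, 1, 2, 3 or more; index stay excluded). Add child age (under 1 year versus older), because infants have a shorter look-back.
2. Report a standardised risk difference with its 95% confidence interval beside the odds ratio.
3. If Aim 4 outcomes by arm have already been seen, keep the primary model and report this as a labelled sensitivity analysis. Do the same for Aim 3, whose results are known.
4. Extend the extract to each Aim 4 child's index admission, and list the pre-index events in the SAP's data management appendix.

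The cost is a longer Aim 4 extract, one derived variable and a few sentences of SAP text. Use outside CCHMC will be missed. Because the covariate is fixed before randomisation, that misclassification should not differ by arm: it weakens the gain but does not bias the comparison.

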The CCHMC pilot nurse home visit program has been offered to families of children receiving care on the Hospitalist Medicine general service. Families receive a *single* nurse home visit within 48 hours of discharge. A nurse provides a comprehensive physical, psychosocial and safety assessment, medication management and a review of the post-discharge care plan including discharge instructions and PCP follow-up with a goal of ensuring that the child is medically stable and the family is comfortable with providing the child's care. The processes of the pilot nurse home visit will be adapted using knowledge acquired in Aim 1 to fully meet the transition of care needs for patients and families not eligible for traditional home health (longer term home visitation services for the medically complex), but who may be at risk for adverse outcomes associated with their hospitalization and an unsupported transition to home.

Quality Improvement Processes

Several co-investigators and collaborators on this project, including physicians, nurses, and parents will work with frontline medical staff (inpatient nurses, home health nurses, and

physicians) as a team to execute the goals of Aim 2. Many of these team members are already working together during this pilot phase.

[figure not shown]
Optimizing Nurse Home Visits: We will review the data from Aim 1 to better understand the barriers patients and families face, as well as the goals or outcomes they value. These data will inform our initial approach and cycles of tests will allow us to refine the discrete outcomes within Aim 2 that we will be targeting. *A priori*, these outcomes will be organized within several domains: clinical outcomes such as health care reutilization, patient/family experience outcomes such as confidence in care at home, and care delivery process outcomes such as medicine reconciliation accuracy or follow-up with PCP. Once initial outcomes are defined, we will specify hypotheses about what is needed to achieve or drive the outcomes. These "key drivers" will then focus subsequent cycles of tests. The team will meet every 1 to 2 weeks with the goal of reviewing data and designing new iterations to be tested on the 5-10 nurse home visits that follow.

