Data for this aim will be collected in-hospital after enrollment, during the nurse home visit, during the follow-up phone call for a subset of families, and though medical record review. On intake, the home visiting nurse will collect information on demographics, indication for the visit, and goals for the nurse home visit mutually-agreed upon by the care team and family. We also believe that there will be iterative qualitative and quantitative elements that the nurses may address during the home visit, which will be defined based on the focus groups in Aim 1. Clinical research coordinators (CRCs) will review the medical record of each patient that was referred for a nurse home visit to assess if medication reconciliation occurred at the follow-up visit, if the mutually-agreed upon goals were addressed at the visit, and if the patient had any unplanned hospital, ED, or outpatient utilization. Assessing unplanned utilization for all patients will be limited to reviewing CCHMC billing data, but we plan to compare hospital billing data to parent report for the subsample of patients that receive a follow-up call. The follow-up call, completed 31-45 days after the admission, will also assess parental confidence, if the family followed up with the PCP or subspecialist, and other iterative qualitative and quantitative elements that will be defined based on the findings from Aim 1. All data and follow-up phone call surveys will be entered into a password protected electronic database.

We will measure and track a core set of outcome measures from key outcome 3 domains of clinical, patient and family experience, and care delivery processes throughout Aim 2. The core clinical outcome measure will be 30-day post-discharge health care reutilization, defined for this Aim as readmission to the hospital or revisit to the ED. The core patient and family experience outcome measure will be an assessment of the family's comfort in managing care of the patient at home, completed at the end of the nurse home visit. Measured on a 5-point Likert scale, this single question will also be asked before hospital discharge by the home visit nurse to establish a family baseline. The core care delivery process measures will focus on two key processes: medicine reconciliation- measured by the number of clarifying actions or adjustments the home

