For both the home visits and the phone calls, we will evaluate the effects of adaptations on measures using statistical process control (SPC) methods. SPC is an analytic method originating in industrial engineering for assessment of the control of a process within targeted parameters. In this proposal, the *a priori* core measures will be tracked and plotted graphically in time series fashion using run and Shewart (control) charts. We will assess the stability of each measure by obtaining baseline data for at least 20 visits prior to adaptation and will use SPC principles to determine when a change in the home visit process leads to a meaningful change in the measures, known as special cause variation. 42,43 The graphical nature of SPC makes it ideal for the evaluation of frequent changes in a process; in contrast to traditional pre-post intervention analyses which are based on data aggregation (such as average values), SPC displays individual data points for maximum visualization of variation over time. Further, SPC provides immediate feedback as data is collected regarding the effectiveness of adaptations to meet desired goals. The steps of analysis include 1) evaluation of baseline data for each of the three core measures; 2) establishment of control limits to help determine when a change in the intervention results in a meaningful change in measures; 3) weekly sequential plotting of visit-level data; and 4) weekly evaluation by research team to determine when special cause has occurred and which adaptation precipitated the cause.

Aim 3

All primary analyses will include the intent to treat population.

Working hypothesis 1: Patients who receive the nurse home visit intervention will have a significantly lower occurrence of any all cause rehospitalization, ED/urgent care revisit, and/or unscheduled follow-up within 30-days post-discharge when compared to the patients enrolled in the control group after 30 days post-discharge. The dependent variable will be a dichotomized indicator of any occurrence of rehospitalization, ED revisit, and/or unscheduled follow-up within 30-days post-discharge. Differences in this outcome between intervention and control groups will be evaluated using logistic regression with the stratification variable (presence or absence of underlying chronic condition and hospitalist medicine general vs. surgical service) included in the model to account for the sampling design.

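### Weekly control-chart review in Aim 2 cannot say which adaptation changed 30-day reutilization: each is tested on 5-10 visits and the outcome is complete about two to four cycles later

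*Protocol*

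**What the plan says.** The protocol's Study Procedures for Aim 2 define the clinical measure as follows: "core clinical outcome measure will be 30-day post-discharge health care reutilization, defined for this Aim as readmission to the hospital or revisit to the ED". Besides this, the core measures are family comfort at the end of the visit, clarifying actions during medicine reconciliation, and whether key needs were addressed.

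Data Analysis/Methods, Aim 2, covers both home visits and phone calls. The "core measures will be tracked and plotted graphically in time series fashion using run and Shewart (control) charts". Stability is assessed by "obtaining baseline data for at least 20 visits prior to adaptation". The analysis then proceeds by "weekly sequential plotting of visit-level data", and its last step is "weekly evaluation by research team to determine when special cause has occurred and which adaptation precipitated the cause". The same paragraph says that the method gives immediate feedback on whether adaptations work. It makes no exception for reutilization, and gives no subgroup size, signal rule or allowance for the 30-day window.

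Study Design, Aim 2 (Optimizing Nurse Home Visits) sets the pace: "The team will meet every 1 to 2 weeks with the goal of reviewing data". Each such meeting also aims at "designing new iterations to be tested on the 5-10 nurse home visits that follow".

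**The concern.** Attributing a signal to one adaptation needs two things. The visits made under that adaptation must carry enough information to signal, and their outcomes must be known before the next adaptation replaces it. Comfort, medicine clarifications and needs addressed are known at the visit, so timing is no obstacle for them. An uncommon yes/no outcome with a 30-day window has difficulty with both. At stake is what the Aim 2 charts may be said to show about reutilization. Aim 2 shapes the interventions tested in Aims 3 and 4, both of which have 30-day reutilization as primary outcome.

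**Working it through.** **Expected rate.** The inputs are in the Aim 3 sample-size paragraph: readmission 5% (general service) and 15% (surgical), 10% surgical share, ED revisit 10%, outpatient use 4%.
- Readmission: 0.9 × 5% + 0.1 × 15% = 6%. Adding 10% and 4% reproduces the protocol's 20%.
- The Aim 2 measure omits outpatient use: 6% + 10% = 16%, or 5% + 10% = 15% on the general service alone. Overlap between readmissions and ED revisits would lower it.

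**One adaptation, 5-10 visits.** Three-sigma limits are p ± 3√(p(1−p)/n).

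| p | n = 5 | n = 10 | Visits per point for a lower limit above 0: n > 9(1−p)/p |
|---|---|---|---|
| 0.15 | −0.33 to 0.63 | −0.19 to 0.49 | more than 51 |
| 0.16 | −0.33 to 0.65 | −0.19 to 0.51 | more than 47 |
| 0.20 | −0.34 to 0.74 | −0.18 to 0.58 | more than 36 |

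No batch of this size can fall below its lower limit, even with zero events. Two-sigma limits do not help: they need n > 4(1−p)/p, which is more than 22 visits at 0.15, 21 at 0.16 and 16 at 0.20. The chance of no events with no improvement is (1−p)^n. That is 0.44 (n = 5) and 0.20 (n = 10) at 15%, and 0.42 and 0.17 at 16%. A run chart of single 0/1 visits has median 0, so no point can lie below it.

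**Baseline.** Twenty visits at 15-16% give 3.0 to 3.2 expected events. The exact 95% interval for 3/20 is 3% to 38%.

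**Lag.** The outcome is complete 30 days after discharge: 30/14 = 2.1 cycles at two weeks per cycle, 30/7 = 4.3 at one week. Counted instead from a visit 2-4 days after discharge, 26-28 days remain, or 26/14 = 1.9 to 28/7 = 4.0 cycles. The parent call, 31-45 days after admission, does not change this materially.

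**Runs over many batches.** Assume a signal is 8 consecutive points below a correctly placed centre line, 10 visits per point and a baseline of 15%. A point is below the line if it has 0 or 1 event.

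| True rate | P(point below line) | One given set of 8 points | At least one run in 20 points (200 visits) | In 40 points (400 visits) |
|---|---|---|---|---|
| 15% (no change) | 0.544 | 0.008 | 5% | 12% |
| 9.75% (35% fall) | 0.746 | 0.10 | 38% | 67% |
| 7.5% (halved) | 0.830 | 0.23 | 64% | 91% |

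With up to 600 home-visit families, a sustained large fall could be seen. Eight points of 10 visits are 80 visits, however, and at one adaptation per batch they cover eight adaptations.

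**Visits between events.** With g = (1−p)/p, the upper limit is g + 3√(g(g+1)). At 15% this is 24.1, so 25 event-free visits in a row are needed: 0.85^25 = 0.017 by chance per gap, 0.925^25 = 0.14 if the rate halves. That again spans several batches of 5-10.

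**The case against.** The strongest reply is that 5-10 visits is the size of a test, not a stated chart subgroup. The protocol names run charts and visit-level plotting, so a visits-between-events chart is not excluded. An effective element that is kept goes on acting in later versions, so its effect can accumulate into a detectable run. Outcomes ordered by visit also stay attached to the version that produced them, however late they arrive.

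Much of this stands. A reader might infer that Aim 2 cannot detect any fall in reutilization. The documents do not support that, as the run probabilities show. What does not survive is attribution: a run or a long event-free gap extends over several adaptations, and the chart cannot separate them. The delay remains as well, even if the late outcomes are filed correctly.

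Three other inferences are tempting and unsupported:
- *Elements were kept or dropped on noise.* A chart that seldom signals mostly prompts no action. The adaptations also draw on Aim 1 findings, key drivers and measures known at the visit.
- *A rise would be missed.* At 15% and n = 10 the upper limit is 0.49, so five or more events in ten visits would signal, with about a 1% chance of doing so with no change. Individual events can also be seen before day 30.
- *Aims 3 and 4 are biased, or the higher odds of revisits reported for Aim 3 are explained.* Aim 2 is intervention development. Its charts do not enter the randomised comparisons, and nothing here accounts for the Aim 3 result.

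**Conclusion.** The concern holds for 30-day reutilization and for the claim of immediate, adaptation-specific feedback. At every rate the protocol's figures support (15% to 20%), a batch of 5-10 visits has a negative lower limit, and complete outcomes come about two to four cycles late. What remains possible is a slow, bundle-level signal. Its probability depends on assumptions the protocol does not state: the 8-point rule, 10 visits per point, a sustained fall and a well-placed centre line, which 20 baseline visits do not secure. Weekly review of the measures known at the visit is not affected by the lag.

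This should be corrected because it is a stated rule that cannot work for one core measure. It does not threaten the validity of either randomised trial. The protocol already describes the home-visit optimisation as successful, so for that part the correction governs how its reutilization charts are interpreted and reported.

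**What to change.** In Data Analysis/Methods, Aim 2:
1. Limit the weekly decision on which adaptation caused a signal to measures known at the visit: comfort, medicine clarifications and needs addressed.
2. Chart reutilization separately, ordered by discharge date, with each visit entered only after 30 complete days. State in advance either a run rule or a visits-between-events chart, with its false-alarm rate. Under the assumptions above, that is 5% within 20 points for the 8-point rule at n = 10, or 1.7% per gap for the visits-between-events chart. Use the chart only to judge the cumulative bundle.
3. Remove the claim of immediate feedback for this measure.
4. For the phone-call optimisation (up to 150 families, feedback call 1-7 days later), do not use reutilization to attribute adaptations.

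Pooling into fixed cohorts of just over 50 visits is not a good substitute. At 15% and n = 52 the lower limit is 0.0014, so only a cohort with no events would signal. If the rate halves, that has probability 0.925^52 = 0.017 per cohort, or 1 − (1 − 0.017)^11, about 18%, over the 11 cohorts that 600 families allow.

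The cost is a paragraph of text and a second chart template. The downside is a later signal for reutilization that speaks to the bundle and not to its parts.
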